## 6.2 Statistical Models

Subgroups will be defined based on the above factors and. Estimates of treatment effects in terms of adjusted ORs and 95% CIs will be obtained separately in all subgroups using logistic regression models adjusting for the study arm and the sites. We will not include the other stratifying variables or unbalanced covariates in these subgroups analysis because they themselves will also serve as subgroups to be compared. In short, for all subgroup analysis, we will apply a consistent modeling framework adjusting only for the study arm and the sites.

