## 5.4 Randomization

Up to 1000 patients will be recruited, with patients randomized to PN or mDOT in a 1:1 ratio (500 subjects in each group) in variable block sizes of 2-6 via central, computer-generated randomization provided by the UNM Statistical and Data Coordinating Center (SDCC). Randomization will occur in blocks to ensure comparison groups of approximately equal size. Given that the intervention will not be blinded, block size will vary to prevent anticipation of treatment arm assignment.

Two special randomization strategies (stratification and blocking) will be used to avert imbalances in prognostic factors or treatment settings, and to ensure comparison groups of approximately equal size. Participants will be stratified by 3 factors: city, OTP vs. community health center and stage of liver disease (cirrhosis v. no cirrhosis).

In addition, adaptive re-weighting of random allocation in a pseudo urn randomization fashion will be made when N~300 has been enrolled to balance the sample size between mDOT and PN arms. Specifically, as we hypothesize that number of randomized subjects who will initiate treatment will be larger in the PN arm, unbalancing between arms is likely to occur during the course of the study. Of note, therefore, a randomized subject will not necessarily be a clinical treatment subject but will be included in the comparison of treatment initiation.

To adjust for this potential unbalance, we will adjust randomization based on observed allocation ratio at the middle of trial if the overall allocation difference is greater than 5% (i.e., <47.5% vs. 52.5%).

Storage and dispensing of random allocation codes will be made in a centralized fashion. The UNM SDCC will generate and store the codes for all sites and types of clinics, and will be embedded into the Research and Electronic Data Capture (REDCap) data management system in the backend so that the identification of a treatment assignment will be ready and immediate without contacting the coordinating center when requested through the REDCap electronic request form by a responsible research staff at the sites whenever a new eligible participant is enrolled. The UNM SDCC will also be responsible for conducting re-weighted randomization, if necessary, at the middle of the trial.

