#### 5.4 Statistical Model

Multivariable logistic regression will be applied to test the overall effectiveness of DOT or PN on the SVR (success vs. failure) as the primary outcome. The arm indicator will serve as the primary predictor. The CONSORT and ICH-9 statistical analysis guidelines suggest that, any baseline characteristics, even if significantly unbalanced between arms, should not be included in the multivariable logistic model since baseline imbalance could be due to chance rather than systematic bias in randomized studies but include as the covariates the randomization stratification variables. In the HERO study, they are: site/city, clinic type (OAT and CHC) and stage of liver disease (cirrhosis vs no).

The primary mITT sample, nonetheless, might no longer represent a randomized pool of participants since the characteristics of participants who initiated treatments may be unequal between the two models of care which may have differential effects on triggering treatment initiations due to difference in modalities of treatment initiation and delivery. Therefore, there could exist baseline characteristics that are unbalanced beyond chance among initiated participants between the two arms. We will declare imbalance if a baseline characteristic is significantly different between the two arms with a two-sided p-value < 0.01 considering the multiplicity of testing. As such, we will include unbalanced baseline characteristics for adjusting purposes in multivariable models in addition to the randomization stratification variables, resulting in the following model:

$$\text{Logit}(P(\text{SVR})) = b_0 + b_1 * \text{TRT} + b_2 * \text{Site1} + \dots + b_8 * \text{Site7} + b_9 * \text{Clinic\_Type} + b_{10} * \text{Cirrhosis}$$

+ Unbalanced Covariates

We will consider exploring other methods to adjust potential imbalance using propensity scores or inverse probability weighting.

For the analysis of the secondary ITT sample, we will only include the randomization stratification variables following the CONSORT and ICH-9 statistical analysis guidelines since the ITT samples are purely randomized participants, resulting in the following model:

$$\text{Logit}(P(\text{SVR})) = b_0 + b_1 * \text{TRT} + b_2 * \text{Site1} + \dots + b_8 * \text{Site7} + b_9 * \text{Clinic\_Type} + b_{10} * \text{Cirrhosis}$$

For the analysis of PP model the approach applied to the analysis of the mITT sample will be applied.

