Review of the monthly enrollment reports during the conduct of the study, however, consistently revealed that few participants have cirrhosis to the extent that there are sites and clinics without any randomized participants with cirrhosis. This imbalance raises a concern with respect to the logistic model fitting which may not result in convergence in regression coefficient estimation algorithms due to a potentially ill-conditioned data matrix. If this occurs, we plan to

remove the cirrhosis term in the above model and fit the following model as the primary multivariable model that include only sites and clinic types for adjusting purpose.

$$\text{Logit}(P(\text{SVR})) = b_0 + b_1 * \text{TRT} + b_2 * \text{Site1} + \dots + b_8 * \text{Site7} + b_9 * \text{Clinic\_Type}$$

+ Unbalanced Covariates

We will report the adjusted odds-ratio (OR) with a 95% confidence interval (CI) for the estimate of the DOT vs. PN effect on SVR. We will also compute 95% CIs for the overall and arm-specific SVR rate using an exact (Clopper-Pearson) method to compare with results from other trials. Again, this analysis will be repeated for each of the three analytic samples albeit with different adjusting variables depending on the constituency of the samples: mITT, ITT and PP.

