### 6.1 Subgroups to be compared

The primary subgroups and their levels are as follows:

- Demographic factors:
  - Sex: Males vs. Females
  - Age: <30 vs.  $\geq 30$
  - Race/Ethnicity: African American vs other; White vs. Other
  - Ethnicity: Latino (Yes vs. No)
  - Employment: Employed vs. Unemployed
  - Education:  $\leq$ HS diploma vs  $>$ HS diploma

- Married/Co-habitating vs. Other
- Housing: Unstable vs. stable
- Ability of transportation vs. Inability
- Clinical factors:
  - Opioid agonist treatment (OAT) clinic vs. community health clinic (CHC)
  - Any medication for OUD in the past 3 months: methadone/buprenorphine vs. none
  - HIV Co-Infection (yes vs. no)
  - HIV viral load: <200copies/mL vs. ≥200copies/mL
  - HCV Genotype (3 vs other)
  - HBV Co-infection: yes vs. no (+ vs. -)
  - Cirrhosis (yes vs. no)
  - Depression (severe/moderate vs. mild/none)
  - Anxiety (severe/moderate vs. mild/none)
  - HCV Treatment naïve vs. experienced
- Alcohol and Drug use:
  - Hazardous alcohol at baseline (yes vs. no)
  - Hazardous alcohol during treatment (yes vs. no)
  - Amphetamine at baseline (UTOX): Yes vs. No
  - Amphetamine during treatment (UTOX): Yes vs. No
  - Benzodiazepine at baseline (UTOX): Yes vs. No
  - Benzodiazepine during treatment (UTOX): Yes vs. No
  - Cocaine at baseline (UTOX): Yes vs. No
  - Cocaine during treatment (UTOX): Yes vs. No
  - THC/Cannabis at baseline (UTOX): Yes vs. No
  - THC/Cannabis during treatment (UTOX): Yes vs. No
  - Opiate at baseline (UTOX): Yes vs. No
  - Opiate during treatment (UTOX): Yes vs. No

- Oxycodone at baseline (UTOX): Yes vs. No
- Oxycodone during treatment (UTOX): Yes vs. No
- Any drug screen + at baseline (UTOX): Yes vs. No
- Any drug screen + during treatment (UTOX): Yes vs. No
- Injecting Behaviors:
  - Last drug injection at baseline: within 5-8 weeks vs 0-4 weeks
  - Last drug injection at baseline: within 9-12 weeks vs 0-4 weeks
  - Times IDU a day at baseline ( $\geq 2$  VS  $<2$ )
  - Times IDU a day during treatment ( $\geq 2$  VS  $<2$ )
  - Times IDU a day at baseline ( $\geq 3$  VS  $<3$ )
  - Times IDU a day during treatment ( $\geq 3$  VS  $<3$ )

Note: Additional subgroup analyses will be conducted based on investigator-driven proposals on concept sheets

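### Subgroup and factor models in SAP 6.2 adjust only for arm and site, so some factor effects may be confounded by clinic type, and mITT and PP subgroup ORs drop any unbalanced covariates

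*SAP*

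**What the plan says.** Protocol 5.4 stratifies randomisation by city, clinic type and cirrhosis. For the mITT sample, SAP 5.4 puts all three in the SVR model and goes further. It warns that "The primary mITT sample, nonetheless, might no longer represent a randomized pool of participants" because the two models of care may trigger initiation differently. It continues: "Therefore, there could exist baseline characteristics that are unbalanced beyond chance among initiated participants between the two arms". Its remedy is that "we will include unbalanced baseline characteristics for adjusting purposes in multivariable models in addition to the randomization stratification variables", with imbalance declared at p < 0.01. The PP sample follows the mITT approach; the ITT model has the strata only. If sparse cirrhosis prevents convergence, SAP 5.4 would "remove the cirrhosis term in the above model and fit the following model as the primary multivariable model".

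The subgroup section uses a smaller covariate set. SAP 6.2 states "In short, for all subgroup analysis, we will apply a consistent modeling framework adjusting only for the study arm and the sites", and gives as its reason that "We will not include the other stratifying variables or unbalanced covariates in these subgroups analysis because they themselves will also serve as subgroups". The formulas agree: 6.2.1 has the subgroup indicator, arm and seven site terms, and 6.2.2 adds the indicator-by-arm interaction. The factors in SAP 6.1 include HIV co-infection and "Any medication for OUD in the past 3 months: methadone/buprenorphine vs. none".

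Protocol 11.10 called for arm-imbalanced confounders in all its models and for subgroup effects estimated by the same methods as the main analysis. The SAP is narrower, and it plans no sensitivity analysis that restores the covariates.

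**The concern.** That a variable is also a subgroup is a reason to leave it out of one model, the one in which it is the indicator. It is not a reason to leave clinic type out of the model for HIV status or for medication.

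Two kinds of estimate are affected differently.

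- **Factor effects** (6.2.1 and the within-arm contrasts of 6.2.2). These factors are not randomised. If a factor is more common in one clinic type, and SVR differs by clinic type, part of the clinic difference is reported as an effect of the factor. These models serve the Protocol 3.3 objective on factors associated with outcome.
- **DOT vs PN within subgroups.** Stratified randomisation should keep clinic type and cirrhosis roughly balanced by arm. What is lost is any covariate that SAP 5.4 adds because initiation may have unbalanced the arms. The mITT subgroups come from that same sample, so the SAP's own argument applies to them.

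**Working it through.** **1. The plan's own subgroup figure.** SAP 6.3 gives a detectable difference of 12 points or more with N=300 in a subgroup, base SVR 80% and adjusting variables explaining 10%. Effective n per arm = 150 × (1 − 0.10) = 135. For 80% vs 92% the pooled rate is 0.86:
- null SE = √(2 × 0.86 × 0.14 / 135) = 0.0422
- alternative SE = √((0.80 × 0.20 + 0.92 × 0.08) / 135) = 0.0416
- power = Φ((0.12 − 1.96 × 0.0422) / 0.0416) = 81.5%

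The difference detectable at 80% power is 11.8 points, so the figure is reproduced. It already allows for adjusting variables.

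**2. Does a listed factor follow clinic type?** Protocol Table 1, printed totals, HIV co-infected:
- OTP: 510 / (4790 + 510) = 9.6%
- CHC: 1433 / (2809 + 1433) = 33.8%

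The CHC rows as printed add to 2864 and 1343, which gives 1343 / 4207 = 31.9%; the contrast stands either way. Site terms do not remove it, because it exists within cities:
- Providence: 25/775 = 3% vs 400/450 = 89%
- Albuquerque: 25/745 = 3% vs 200/220 = 91%
- San Francisco: 70/395 = 18% vs 213/313 = 68%

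It is not uniform. The Bronx (14% vs 13%) and Baltimore (17% vs 9%) show no gap or a reverse one.

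**3. Size of the possible bias in factor effects.** Assumptions: N=600 spread equally over the 16 clinics, 1:1 arms, no arm effect, no true factor effect. HIV prevalence is taken clinic by clinic from Table 1. Medication for OUD is assumed at 90% in OTP and 40% in CHC. SVR by clinic type is assumed. The 6.2.1 model (factor, arm, site) was fitted to the expected cell counts. The false-positive rate is the chance that a two-sided 5% Wald test rejects, given the expected log OR and its SE.

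| Assumed SVR, OTP vs CHC | HIV: OR (false positives) | Medication: OR (false positives) |
|---|---|---|
| 80% vs 80% | 1.00 (5%) | 1.00 (5%) |
| 83% vs 77% | 0.84 (11%) | 1.22 (16%) |
| 85% vs 75% | 0.74 (23%) | 1.40 (36%) |
| 88% vs 72% | 0.63 (49%) | 1.70 (72%) |

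With clinic type in the model, every cell becomes OR 1.00 with 5%.

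Hand check of the medication OR at 85% vs 75%:
- P(OTP | medication) = 0.45/0.65 = 0.692; P(OTP | none) = 0.05/0.35 = 0.143
- SVR = 0.692 × 0.85 + 0.308 × 0.75 = 81.9% with medication; 0.143 × 0.85 + 0.857 × 0.75 = 76.4% without
- OR = (0.819/0.181) / (0.764/0.236) = 1.40

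Softer and harder cases, with clinic-type ORs of 1.5 to 3 and a 50:50 clinic split: the spurious OR is 1.08–1.23 at factor prevalence 60% vs 40%, 1.18–1.53 at 80% vs 40%, and 1.28–1.86 at 95% vs 40%.

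**4. DOT vs PN.** Assumptions: clinic type 50:50 and cirrhosis 21% (Protocol 11.10), both balanced by arm; SVR 80% in PN; clinic-type OR 1.5–3; cirrhosis OR 0.5–1. A conditional OR of 2.10 becomes 2.03–2.09 when both strata are omitted. In the factor set-up of step 3's last paragraph, with clinic type omitted, within-factor treatment ORs of 1.50 become 1.48–1.50. The effect of omitting the unbalanced covariates cannot be computed, because they are not yet known.

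**5. Cost in model terms.** Expected failures = 300 × 0.20 + 300 × 0.11 = 93. The 6.2.2 model has 10 slopes (indicator, arm, interaction, seven sites); clinic type and cirrhosis make 12. Failures per term go from 93/10 = 9.3 to 93/12 = 7.75, before any unbalanced covariates.

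**The case against.** The best defence has five parts.

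- **The treatment contrast is hardly touched by the strata.** DOT vs PN is what SAP 6.2.2 names as its primary interest, and step 4 shows the shift is trivial beside a detectable difference of about 12 points. This stands. A reader might infer that subgroup ORs cannot be compared with the overall OR; omission of the strata does not support that.
- **Confounding is not demonstrated.** Neither document gives SVR by clinic type or medication use by clinic type, and with no clinic effect on SVR the bias is nil. This stands, and it makes the point conditional. The HIV prevalence gap, however, is in the Protocol.
- **The unbalanced set may be empty.** It needs p < 0.01, and the ITT repeat has no such covariates by design. This stands as a limit on size. If the set is not empty, the subgroup models omit what SAP 5.4 calls for.
- **Cirrhosis may be too sparse.** SAP 5.4 foresees removing it from the primary model itself, and reports strata adjustment as something guidelines suggest. This stands for cirrhosis. It does not apply to clinic type, which Protocol 11.10 expects at 50:50.
- **Protocol 3.3 names psychosocial factors**, such as homelessness and mental illness, rather than HIV or medication. True, but SAP 6.1 lists both and plans to test them.

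Nor is every model short of every stratum. Site is always kept, the clinic-type and cirrhosis rows each contain their own variable, and the factor models for resistance and reinfection in Protocol 11.11 are multivariable.

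**Conclusion.** The concern holds in a limited form. The covariate omission in SAP 6.2 is explicit and its stated reason does not justify it. Factor effects in 6.2.1, and within-arm contrasts in 6.2.2, may be confounded by clinic type for factors that differ between OTP and CHC within a city: HIV co-infection on the Protocol's own counts, and plausibly medication for OUD. The size rests wholly on an assumed SVR difference by clinic type. At 85% vs 75% a null factor shows an OR of 0.74 (HIV) or 1.40 (medication); at no difference it shows 1.00. The HIV figures also assume equal enrolment over the 16 clinics and participants who resemble the Table 1 pools.

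For DOT vs PN by subgroup, the only concern is in mITT and PP, where covariates that SAP 5.4 adds against selection at initiation would be dropped. Its size is unknown and could be zero. The overall primary SVR analysis is not affected.

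**What to change.** Change the covariate rule in SAP 6.2 and the formulas in 6.2.1 and 6.2.2:

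- add clinic type to every model except the one in which it is the subgroup indicator;
- add cirrhosis where it can be estimated, with the same removal rule as SAP 5.4, and except where it is the indicator;
- in mITT and PP, add the unbalanced covariates used in the primary model, again except where one is the indicator;
- where a subgroup is too small to carry these terms, keep the arm-and-site model and say so in the table or forest plot.

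The cost is one rewritten paragraph and two formulas; all the variables are already collected. The power stated in SAP 6.3 need not change, since it already assumes adjusting variables that explain 10%. The downside is a thinner model: about 7.75 rather than 9.3 expected failures per term in the interaction model, before unbalanced covariates, and fewer in small rows.

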### 6.2.1 Main subgroup effects

The main effect of subgroup indicators (e.g., OAT vs. CHC) will be assessed via comparing outcome between levels of each subgroup in multivariable models adjusting for the care model arms and site, that is, the multivariable logistic regression model that include: a subgroup indicator, site and the arm indicator in the following form:

$$\text{Logit}(P(\text{SVR})) = b_0 + b_1 * \text{Subgroup Indicator} + b_2 * \text{TRT} + b_3 * \text{Site1} + \dots + b_9 * \text{Site7}.$$

The analysis results will be graphically displayed in a forest plot.

### 6.2.2 Assessment of heterogeneity of models care effect across subgroups

The following multivariable model will be used to both: 1) estimate and test DOT vs PN effects in each subgroup (i.e., DOT vs. PN in each of OAT and CHC); and 2) estimate test Subgroups effects in each of DOT and PN arms (OAT vs. CHC in each of DOT and PN arms).

$$\text{Logit}(P(\text{SVR})) = b_0 + b_1 * \text{Subgroup indicator} + b_2 * \text{TRT} + b_3 * \text{Subgroup indicator} * \text{TRT} + b_4 * \text{Site1} + \dots + b_{10} * \text{Site7}$$

The primary interest of this subgroup analysis will be estimating the DOT vs. PN effect on SVR in terms of point (i.e., odds-ratio) and interval estimates (i.e., 95%CI) and testing significance of DOT vs. PN effects in each group. The analysis results will also be graphically displayed in a forest plot. The secondary interest will be testing significance of the interaction term that represents a difference in DOT vs. PN effect on SVR between subgroups.

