## 11.8 Heterogeneity of mDOT or PN effects

The mDOT or PN effects depending on outcome (see Aim 1 hypotheses) will be assessed for each subgroup stratified various factors (e.g., clinic setting, demographic, or clinical), which are specified below, and will be compared across the subgroup strata. Forest plots will be produced to show graphically the differences or contrasts in effect sizes across all subgroups. Formal tests will follow via testing significance of pertinent interaction terms with the mDOT or PN arm indicator in statistical models.

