### **Subgroup Heterogeneity Analyses**

To assess heterogeneity of mDOT or PN effects, additional analyses will be conducted to evaluate whether the mDOT effect varies by variety of subgroups stratified by the following characteristics: OTP (50%) vs. CHC (50%); Males (70%) vs. Females (30%); Patients using illicit drugs during treatment (65%) vs. those not using illicit drugs (35%); HIV/HCV coinfected (28%) vs. HCV mono-infected (72%); Cirrhosis (21%) vs. non-cirrhosis (79%); African American / Latino (41%) vs. Caucasian (59%); Marginally housed (26%) vs. stably housed (74%); Comorbid mental illness (55%) vs. no mental illness (45%); and Peer-support (70%) vs. no peer-support (30%). Initially, subgroups will be defined based on the above factors and estimates of treatment effect will be obtained separately in each subgroup using the methods described above. The significance of any heterogeneous mDOT or PN effects across these factors will be formally tested by testing significance of corresponding interaction terms with the mDOT or PN arm indicator. In addition, we will also conduct within-arm subgroup analyses to identify factors that are associated with outcomes within arms. For example, one test would be if increased social support will be associated with higher treatment initiation within the PN arm.

**Power analysis for subgroup analysis:** For the subgroup analysis, the minimally detectable effect size will depend on the sample size of subgroups. However, assuming that a subgroup has 50% of the total sample, i.e., N=270, and that a base outcome rate is 80% (e.g., SVR), then  $\geq 12\%$  difference will be detected using a Chi-square test. The minimally detectable standardized effect size for continuous outcome will be 0.3. This power analysis also applies to detect binary or continuous factors associated with outcome from within-arm subgroups analyses since the sample size of each arm will be N=270 after attritions. For the subgroups with smaller sample size, the minimally detectable effects sizes, binary or continuous, will be larger. For example, for some of our subgroups will be as small as 20% (or, N= 108) of the sample (e.g. HIV/HCV coinfected), minimum effect sizes are larger at  $\geq 17\%$  for SVR and 0.5 standardized effect size for continuous variables.

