## 6 Subgroup Analysis

Subgroup analysis will be conducted to assess potential heterogeneity of models of care effect across the levels of subgroups (section 6.1). The subgroup analysis will estimate and test: 1) main subgroup effect (section 6.2.1); and 2) the interaction between subgroup and the models of care to assess both between-arm and within-arm subgroup effects (section 6.2.2).

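### SAP 6.2.2 ranks DOT vs PN significance tests within subgroup levels above the interaction test that protocol 11.8 and 11.10 make the formal test of heterogeneity; ten SAP 6.1 contrasts are measured during treatment

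*SAP*

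**What the plan says.** SAP section 6 states the purpose: "Subgroup analysis will be conducted to assess potential heterogeneity of models of care effect across the levels of subgroups". Section 6.2.2 fits a logistic model with subgroup, arm, their product and site, then ranks what is read from it. The primary interest is the DOT vs PN odds ratio with its 95% CI in each level, together with "testing significance of DOT vs. PN effects in each group". The interaction comes next: "The secondary interest will be testing significance of the interaction term that represents a difference in DOT vs. PN effect on SVR between subgroups".

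Protocol 11.8 has the same components but gives the interaction more authority. It starts with subgroup effects and a display: "Forest plots will be produced to show graphically the differences or contrasts in effect sizes across all subgroups". It continues: "Formal tests will follow via testing significance of pertinent interaction terms with the mDOT or PN arm indicator in statistical models". Protocol 11.10 (Subgroup Heterogeneity Analyses) has the same order. First, "estimates of treatment effect will be obtained separately in each subgroup using the methods described above"; then heterogeneity is to be "formally tested by testing significance of corresponding interaction terms with the mDOT or PN arm indicator".

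SAP 6.1 lists the subgroups under the name primary subgroups and lets investigators add more through concept sheets. Protocol 11.10 names nine factors, among them illicit drug use during treatment, and peer support. SAP 3.3 sets two-sided 0.05 for all testing. Only the SAP's mediation section (section 7) is titled exploratory.

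**The concern.** Whether DOT works differently in two kinds of participant is answered by comparing the two effects, which is what the interaction term does. Two separate significance tests do not make that comparison. One level can cross 0.05 and the other miss it although the effect is identical in both, because each level has limited power and often a different size. Ranking the within-level tests first, under a heterogeneity heading and across a long list, invites a reading such as: DOT works in OTP patients but not in CHC patients.

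The second issue concerns the subgroups themselves. Some are defined by drug use, alcohol use or injecting during treatment. If the model of care changes that behaviour, DOT users and PN users during treatment are no longer comparable groups, and a DOT vs PN contrast within them loses the protection of randomisation.

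**Working it through.** **1. Counts from SAP 6.1.** Demographic 9 bullets (10 contrasts, as the race bullet holds two), clinical 10, alcohol and drug 16, injecting 6. Bullets: 9 + 10 + 16 + 6 = 41. Contrasts: 10 + 10 + 16 + 6 = 42. Measured during treatment: alcohol 1 + urine toxicology 7 + injecting frequency 2 = 10. Each of these ten has a listed baseline counterpart, so 42 - 10 = 32 contrasts use baseline factors.

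**2. The plan's own figure.** SAP 6.3 says a difference of at least 12 points is detectable in a subgroup of N=300 (150 per arm, base SVR 80%, adjusting variables explaining 10% of variation in the predictor). Effective n per arm = 150 × 0.90 = 135. Power = Φ{[d√n - 1.96√(2p̄(1-p̄))] / √(p1q1 + p2q2)}. For 80% vs 92%: [0.12 × 11.62 - 1.96 × 0.491] / 0.483 = 0.895, giving power 81.5%. The smallest difference with 80% power is 11.85 points, so the figure reproduces. It concerns a within-level contrast; SAP 6.3 gives no power for the interaction.

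**3. Same effect in both levels (80% vs 89%, the planned difference in SAP 5.5), N=600.**
- 50/50 split, 150 per arm per level, same formula without the 10% reduction: [0.09 × 12.25 - 1.96 × 0.512] / 0.508 = 0.195, power 57.7%. Exactly one level significant: 2 × 0.577 × 0.423 = 48.8%.
- 20/80 split, 60 and 240 per arm: powers 27.3% and 77.9%. Exactly one: 0.273 × 0.221 + 0.779 × 0.727 = 62.7%.

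A simulation (400,000 trials per cell, Wald tests on the log odds ratio, PN 80%, no site terms) gives:

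| True uniform difference | Exactly one level significant, 50/50 | Same, 20/80 | Interaction falsely rejects, 50/50 to 20/80 |
|---|---|---|---|
| 0 points | 9% | 9% | about 5% |
| 5 points | 32% | 34% | about 5% |
| 9 points | 49% | 64% | 4-5% |
| 12 points | 24% | 55% | 4-5% |
| 15 points | 3% | 32% | 3-4% |

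At 15 points with a 50/50 split the order reverses: 3.2% against 4.1%.

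**4. Interaction power, effect in one level only (80% vs 89%, no effect in the other), N=600.** The log odds ratio is 0.704. For a 50/50 split the variance is 3/(150 × 0.16) + 1/(150 × 0.0979) = 0.193, so the SE is 0.439. Power = Φ(0.704/0.439 - 1.96) = 36%. By simulation it is 28% if the effect sits in a 28% level and 22% in a 20% level.

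**5. Number of tests with no effect anywhere.** The 42 contrasts give 84 within-level tests, with about 84 × 0.05 = 4.2 expected false positives; the 32 baseline interactions give 32 × 0.05 = 1.6. Simulating all factors in the same 600 participants, with assumed factor correlation from 0.6 down to 0, the chance of at least one is 61-75% for the 84 and 61-80% for the 32.

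**6. On-treatment subgroups: an illustration.** Everything here is assumed except 65% drug use (protocol 11.10). Two equal groups have SVR 90% and 70% with no arm effect, and PN drug use is 50% and 80%. SVR among PN non-users = (0.25 × 0.9 + 0.10 × 0.7)/0.35 = 84.3%. If DOT lowers use in the second group from 80% to 60%, SVR among DOT non-users = (0.25 × 0.9 + 0.20 × 0.7)/0.45 = 81.1%. That is a spurious difference of -3.2 points. If DOT does not change use, the difference is zero.

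**The case against.** The case against is substantial, and much of it stands.

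- **Within-level effects are a stated aim.** Protocol 3.2 asks for PN vs mDOT differences in specific sub-populations, and protocol 11.10 powers such contrasts. Estimating them is legitimate, and the fix keeps them.
- **The interaction test is not dropped.** A reader might infer from its rank that it is, or that heterogeneity will be declared when one level is significant and the other is not. Neither is in the documents: SAP 6.2.2 fits and tests the interaction, and no section gives a rule for declaring heterogeneity. The frequencies in step 3 describe how often a misreading would be available. They are not an error rate of a planned decision rule.
- **The comparison is not universal.** Within-level discordance is not always commoner than false interaction rejection, as the 15-point, 50/50 case shows.
- **On-treatment subgroups began in the protocol.** Illicit drug use during treatment is one of its nine factors. Peer support may be another post-randomisation factor, since protocol 6.3 describes optional groups with logged attendance. A reader might infer that the on-treatment contrasts are biased. The documents do not show that. Protocol 11.10 analyses change in illicit drug use, but does not say explicitly that this is by arm, and it also uses substance use as an adjustment variable.
- **Primary subgroups may be a loose label.** It may only separate the listed subgroups from later additions.

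What remains is the rank. Under a heading and purpose that both name heterogeneity, the SAP puts first the test that does not address it, contrary to the protocol's designation of the formal test.

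**Conclusion.** The point holds as a discrepancy in rank and in the choice of effect modifiers, and should be corrected. At the planned 9-point effect, if uniform, about half to two-thirds of contrasts (49-64%) would show one significant and one non-significant level, against 4-5% false interaction rejections; with no effect the figures are 9% and 5%. These rest on PN SVR of 80%, N=600, splits from 50/50 to 20/80, and unadjusted Wald tests.

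For the ten on-treatment contrasts in SAP 6.1 and the protocol's drug-use subgroup, and possibly its peer-support subgroup, the loss of protection by randomisation is a matter of design. The size of any resulting bias is unknown and may be zero; the 3-point illustration depends on invented inputs and is not an upper limit. The primary SVR comparison is unaffected.

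**What to change.** In SAP 6.2.2, state that any claim of heterogeneity rests on the interaction test, as in protocol 11.8 and 11.10, and report within-level odds ratios with 95% CIs as estimates. In SAP 6.1, limit effect-modifier subgroups to baseline factors, using the counterparts already listed, and keep on-treatment drug and alcohol use as descriptive, non-causal associations. Treat the drug-use and peer-support subgroups of protocol 11.10 in the same way unless they are defined at baseline, and record that change. Label all subgroup results exploratory, including concept-sheet additions, and state how many interaction tests were run.

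The cost is wording, with no new data or sample size, but there are three real downsides. Interaction power is low (22-36% in step 4), so a non-significant interaction must not be read as a uniform effect. The chance of at least one false positive is not reduced (step 5), although the expected number falls from about 4 to 1.6; this is why the exploratory label is needed. And whether DOT offsets active drug use, a fair question given the HIV DOT trial described in protocol 2.2, would be examined as effect modification only through baseline use.
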